9.4.3 ANALYSIS OF THE SECONDARY ENDPOINT(S)

SPIRIT effect on advance directive completion (secondary aim): This analysis will be limited to patients who did not have an advance directive at the time of enrollment. For this binary outcome (completed or not completed) measured post intervention, the probability of completion will be estimated for the three groups using logistic regression. Baseline characteristics that differ across groups will be adjusted. Adjusted group mean proportions of completion will be compared between the groups; adjustments for multiple comparisons will be made using Tukey's test.

Surrogates' perceived impact (secondary aim): As in our previous work,¹²⁶ qualitative analysis will use content and thematic techniques.¹²⁷ Initial coding involves line by line examination, labeling, and organizing of data into segments, preserving detail in participants' words.¹²⁸ To optimize validity, codes and definitions will be reviewed and refined by the research team and applied to subsequent interviews.¹²⁹ Related codes will be grouped into categories representing aspects of the surrogates' experiences. Similarities, differences, and trends across cases will be examined.¹³⁰ Then, data will be organized into themes. This work will be done by Drs. [name] and [name] and the project director; discrepancies will be resolved by consensus. To explore differences in themes by AD progression and by treatment condition, we will count the occurrence of themes ("quantitizing")^{131,132}; the occurrence of each theme will be counted only once for a participant even if it is mentioned more than once. The data will be graphed to facilitate pattern interpretation.¹³³

9.4.4 SAFETY ANALYSES

Not applicable.

9.4.5 BASELINE DESCRIPTIVE STATISTICS

See 9.4.1 General Approach.

9.4.6 PLANNED INTERIM ANALYSES

Not applicable.

9.4.7 SUB-GROUP ANALYSES

In order to evaluate whether the SPIRIT has differential effects according to demographic factors such as age, sex, race/ethnicity we consider the same generalized mixed effects model, mentioned in Section 9.4.1. However, because of the small sample size, our sub-group analyses will be only exploratory. We will fit the same generalized mixed model by additionally including a subject level factor (e.g., race) and its' interaction with the SPIRIT. We will report p-values and importantly, standard errors and confidence intervals by recognizing the fact that we do not have power to detect significant interaction effects for examining all demographic factor combinations.

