6.2 PREPARATION/HANDLING/STORAGE/ACCOUNTABILITY

6.3 MEASURES TO MINIMIZE BIAS: RANDOMIZATION AND BLINDING

For Stage 1B pilot testing, [name] (statistician/Co-I) will generate a randomization scheme using stratified (by race, white vs non-white study site, Emory vs Grady), permuted block randomization with block size 6, using a random-number generator. Dyads will be randomized with equal allocation (1:1:1) to SPIRIT-in person, SPIRIT-remote, or usual care.

With Revision 14, randomization will be stratified by race (white vs non-white) within recruitment site (Emory, Rush, and Northwestern), with equal allocation to SPIRIT-in person or usual care.

Due to the nature of the intervention, blinding dyads to their group allocation is impossible, but the research staff assessing outcomes will be blind. Immediately after the completion of the baseline assessment by phone, the data collector will open a sealed envelope to identify group assignment and schedule an intervention session to take place ~2 weeks hence for SPIRIT- in person or –remote (with revision 14, all SPIRIT-remote), as well as a follow-up data collection session in the next 2-3 days.

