9.4.2 ANALYSIS OF THE PRIMARY ENDPOINT(S)

SPIRIT effects on the preparedness outcomes: For dyad congruence, a binary outcome (congruent or not congruent), a generalized mixed effects logistic regression model will be used. Specifically, a random intercept model will be used to account for dyad level variation over time while treatment group, time (baseline and post-intervention), and treatment x time interaction will be treated as fixed effects. If there is a significant treatment x time interaction ($\alpha<0.05$) (an overall treatment effect), then two contrasts will be tested for individual treatment effectiveness (usual care vs SPIRIT-in person and usual care vs SPIRIT-remote). Adjustments for multiple pairwise comparisons will be made using Tukey's test. Surrogate DMC and preparedness scores, we will use linear mixed

effects regression models, adjusting for potential covariates as appropriate. Since this is not a non-inferiority trial where two or more interventions that have been proven to be superior to usual care are being compared, the contrast, SPIRIT-in person vs SPIRIT-remote, cannot be tested. However, if superiority of the two modalities to usual care is determined, the estimated group differences could be used for selecting a non-inferiority margin or equivalence range^{124,125} for future studies.

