In light of the changes in study design (V12), we will update the statistical analysis plan. In particular, the preparedness outcomes from the 2-arm and 3-arm RCTs will be analyzed individually to evaluate the effect of the interventions. We will use mixed effects models as mentioned above and use contrasts to compare between the three and two intervention groups respectively. In addition to separate analyses, we will conduct pooled analysis by using analysis of variance methods (ANOVA) and incorporating an indicator variable for study and evaluate the (study x intervention group) interaction effect. We will also explore a meta-analysis approach to obtain a common intervention effect of SPIRIT-remote vs usual-care, from the two studies. If the effect sizes obtained from the individual studies are relatively homogeneous, their individual results may be combined to produce an estimate of the intervention effect. A weighted pooled estimate of effect size can be obtained, using the inverse of each study's variance as the weight. Because the studies are almost identical, we anticipate the variance to be fairly similar in both cases; a fixed effects approach will be used to estimate the variance.

With revision V14: The revised statistical analysis plan will be similar to that described in V12. Our primary aim will be to evaluate the effect of the SPIRIT- remote intervention group versus usual care on the outcomes of interest. We will use generalized linear mixed effect modeling and compare changes in treatment group means or proportions over time using contrasts. Because we only have 3 clusters (sites), fitting a multilevel model would not be feasible. We will instead adjust for site as a fixed effect in our mixed effects model. We will also compare our findings to those from Stage 1A to assess any substantial difference in effect sizes.

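### As written, the subgroup model in 9.4.7 adds factor x SPIRIT but not factor x treatment x time, so its coefficient estimates about half of the differential effect

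*Combined protocol and SAP*

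**What the plan says.** The purpose of 9.4.7 is to "evaluate whether the SPIRIT has differential effects according to demographic factors such as age, sex, race/ethnicity". It does this by refitting the primary mixed model, "additionally including a subject level factor (e.g., race) and its' interaction with the SPIRIT". It names no interaction of the factor with time and no three-way term. It calls the analyses exploratory because the sample is small, admits low power for interactions, and promises p-values with particular weight on standard errors and confidence intervals.

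The model itself is in 9.4.2. There "a random intercept model will be used to account for dyad level variation over time", and the fixed part is treatment, "time (baseline and post-intervention), and treatment x time interaction will be treated as fixed effects". The same section treats that interaction as the test of SPIRIT: "If there is a significant treatment x time interaction ($\alpha<0.05$) (an overall treatment effect"). The V14 text keeps the approach for the two-arm design and will "compare changes in treatment group means or proportions over time using contrasts", with site as a fixed effect.

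Section 9.4.7 cites 9.4.1 as the source of the model. Section 9.4.1 covers descriptive work, baseline comparisons and missing data, and specifies no mixed model.

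**The concern.** If SPIRIT works through a change from baseline to post-intervention, a subgroup difference in its effect is a difference between subgroups in treatment x time, which is factor x treatment x time. The model in 9.4.7, taken at its word, holds the factor-by-treatment difference constant over both time points. Half of what it averages comes from baseline, where there is nothing to find: under 6.3, "Immediately after the completion of the baseline assessment by phone, the data collector will open a sealed envelope to identify group assignment". Baseline therefore precedes allocation, and the expected factor x treatment difference there is zero.

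At stake are the estimates and intervals on which 9.4.7 asks the reader to rely. They would be centred on a fraction of the quantity the section sets out to measure, and nothing in the report would show it. An analyst who coded the sentence literally and one who read it as the three-way term could report estimates differing about twofold from the same data.

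**Working it through.** Section 9.4.7 states no figure to reproduce. The power figure in 9.2 concerns the overall effect on congruence, and this point does not depend on it.

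**Inputs from the documents.** Two time points, a random dyad intercept, and fixed treatment, time and treatment x time (9.4.2); equal allocation and baseline before allocation (6.3); 120 dyads (9.2); all available data analysed (9.3); alpha 0.05 (9.4.2), taken as two-sided because sidedness is not stated.

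**Inputs not in the documents, assumed and varied.** Within-dyad correlation rho 0 to 0.7; factor prevalence 0.5 and 0.3; post-intervention data missing in 0% or 20%; true differential effect 0.8 SD for linear outcomes, or 1.46 log-odds for congruence (ln 4.3, borrowing the odds ratio in 9.2 only as a convenient size).

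**Step 1: what the two-way term estimates.** Let the differential effect be 0 at baseline and d at post-intervention. With complete data on two time points and a random intercept, a term constant over time is estimated from each dyad's mean of its two values. Its expectation is (0 + d)/2 = d/2. The three-way term is estimated from each dyad's change, with expectation d - 0 = d.

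**Step 2: precision in the linear models.** Outcome variance is 1 and each of the four factor-by-arm cells holds 120/4 = 30 dyads.
- Two-way: the variance of a dyad mean is (1 + rho)/2, so SE = sqrt(4 x (1 + rho)/2 / 30) = sqrt((1 + rho)/15).
- Three-way: the variance of a change is 2(1 - rho), so SE = sqrt(4 x 2(1 - rho)/30) = sqrt(4(1 - rho)/15).
- Ratio of test statistics, two-way to three-way: [(d/2)/sqrt((1 + rho)/15)] / [d/sqrt(4(1 - rho)/15)] = sqrt((1 - rho)/(1 + rho)).

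Example at rho 0.5 and d = 0.8: two-way z = 0.4/0.316 = 1.26, power Phi(1.26 - 1.96) = 0.24; three-way z = 0.8/0.365 = 2.19, power Phi(2.19 - 1.96) = 0.59.

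| rho | ratio of test statistics | power, two-way as written | power, three-way |
|---|---|---|---|
| 0 | 1.00 | 0.34 | 0.34 |
| 0.3 | 0.73 | 0.27 | 0.46 |
| 0.5 | 0.58 | 0.24 | 0.59 |
| 0.7 | 0.42 | 0.22 | 0.81 |

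The ratio column does not depend on d. The power columns do.

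**Step 3: simulation, linear outcomes** (120 dyads, 2,000 runs per setting, true value 0.80).
- Complete data: the two-way term averages 0.39-0.41, about half, at every rho and both prevalences. The three-way term averages 0.79-0.83.
- 20% of post-intervention values missing: the two-way term averages 0.33-0.36, or 41-46% of the truth. Dyads with only a baseline value stay in the analysis and pull it towards zero. The three-way term averages 0.79-0.81.

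**Step 4: simulation, dyad congruence** (logistic model with a random intercept, true value 1.46).
- Large-sample fits (10 runs of 4,000 dyads per setting, random-intercept SD 0.5 to 2): two-way 0.51-0.77, or 35-53% of the truth; three-way 1.34-1.60.
- Power at 120 dyads (300 runs): 0.20 as written against 0.24 for the three-way term at random-intercept SD 0.5, and 0.18 against 0.25 at SD 1. That is 4-7 points, and each power has a simulation error of about sqrt(0.25 x 0.75/300) = 0.025.

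**The case against.** The strongest objection is that the phrase is shorthand. Section 9.4.2 identifies the SPIRIT effect with treatment x time, V14 compares changes over time, and 9.4.7 says it wants differential effects. Interaction with SPIRIT can then fairly be read as interaction with the SPIRIT effect, which is the three-way term. On the literal reading, the V14 change contrast would be identical in every subgroup on the model scale, which defeats the section's purpose. This reading is possible, and it bars any claim that the investigators intend the two-way model. But the text does not state it, and an analyst who codes the sentence as it stands gets the wrong term.

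The second objection is that the analyses are exploratory and declared underpowered. That limits the severity. It does not cure the estimate: a caveat about precision does not tell the reader that the interval is centred on the wrong quantity.

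A reader might also infer a large and general loss of subgroup power. The documents do not support that. At an assumed 1.0 SD differential effect, equal subgroups, no missing data and rho 0.5, the closed form gives about 35% against 78%. None of those inputs is in the plan, and 9.2 calls the short-term effect on surrogate confidence negligible (Cohen's d = .02). At rho 0 nothing is lost, and for congruence the difference is small, with both versions badly underpowered.

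**Conclusion.** Wrong as written; low severity. Read literally, the model in 9.4.7 estimates half of the differential effect for surrogate confidence and surrogate preparedness when data are complete. This follows from the two-time-point design and the timing of baseline, and does not depend on the correlation or the prevalence of the factor. The 41-46% figure rests on an assumed 20% missing post-intervention data, and the 35-53% for congruence on assumed effect sizes and intercept variances. It would be wrong to call half exact for every endpoint.

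The power consequence is conditional. It requires positive within-dyad correlation, and its size cannot be fixed from the documents. Nor does the point reach the main results: the primary contrast in 9.4.2 is unaffected, and no primary or secondary conclusion uses the subgroup model. The reference to 9.4.1 is an error on either reading of the sentence.

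**What to change.** In 9.4.7, state that the subgroup model adds factor, factor x time, factor x treatment and factor x treatment x time to the model of 9.4.2, and that the reported quantity is the three-way contrast with its 95% confidence interval. If the analysis is instead specified as a post-intervention comparison adjusted for baseline, factor x treatment is the right term and no three-way term is needed. Change the cross-reference from 9.4.1 to 9.4.2.

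The cost is about one sentence and one section number in the SAP. No new data are needed, and sample size and the primary analysis do not change.

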9.4.8 TABULATION OF INDIVIDUAL PARTICIPANT DATA

Individual participant data will be listed by measure and time point.

9.4.9 EXPLORATORY ANALYSES

None.

10 SUPPORTING DOCUMENTATION AND OPERATIONAL CONSIDERATIONS

10.1 REGULATORY, ETHICAL, AND STUDY OVERSIGHT CONSIDERATIONS

10.1.1 INFORMED CONSENT PROCESS

10.1.1.1 CONSENT/ASSENT AND OTHER INFORMATIONAL DOCUMENTS PROVIDED TO PARTICIPANTS

Consent forms describing in detail the study intervention, study procedures, and risks are given to the participant and written documentation of informed consent is required prior to starting intervention/administering study intervention. Prior to going through the informed consent process with a potential participant, a study team member must receive permission to approach the potential participant. This permission may occur as a verbal consent given to a third party (e.g. medical provider or facility staff member) or as a refrain from returning a pre-paid opt-out post card (after receiving an introductory letter). Study staff will then approach potential participants who have consented to being approached (either in person at the clinic or via telephone). Potential participants who agree to be approached by a study staff member will receive the opportunity to screen and consent to the study (if eligible). Once potential participants have demonstrated that they meet all eligibility criteria through the screening process, they may enroll in the study. The following consent materials are submitted with this protocol.

- Patient Consent Form Phase I (Stage 1A)
- Surrogate Consent Form Phase I (Stage 1A)

- Surrogate Verbal Consent Form Phase I (Stage 1A)
- Patient Consent Form Phase II (Stage 1B)
- Surrogate Consent Form Phase II (Stage 1B)
- Verbal Screening Consent & HIPAA
- Surrogate Verbal Consent Form Phase II (Stage 1B)
- Patient Verbal Consent Form Phase II (Stage 1B)

10.1.1.2 CONSENT PROCEDURES AND DOCUMENTATION

Stage 1A (pre-testing)

Potential patient participants will be those who are currently receiving care from Emory's Brain Health Center located at the Executive Park (2 miles from the School of Nursing). The Brain Health Center encompasses more than 20 clinics which serve a range of neurologic, psychiatric and cognitive conditions. The clinics are staffed by doctors, nurse practitioners, registered nurses, and clinical social workers. Patients who are appropriate for this study may interface with one or more of the clinics to receive services for a diagnosis of dementia.

Study invitation letters signed by Brain Health Center doctors, nurse practitioners, and PI will be mailed to patients with a recent MoCA score ≥ 13 . This letter will explain briefly about the study and include the research staff contact information and an opt-out postcard. After 2 weeks, a research staff member will call potential patient participants who have not returned the opt-out postcard to explain the study further and schedule a brief meeting at the clinic or a convenient location for the dyad. On the day of the meeting, the research staff will review the patient's medical record to confirm the patient's eligibility (a through c) and approach the patient to obtain verbal consent to administer the UBACC to screen the patient for decision-making capacity. With a patient whose UBACC score is equal to or higher than 11 (or 9 or 10 with consultation of PI), the recruiter will determine whether the person accompanying the patient is an appropriate surrogate decision-maker using the Surrogate Selection Guide. Written or verbal consent will be obtained from each member of the dyad.

Stage 1B (formal pilot testing)

Participants will be recruited from: Emory's Brain Health Center, Emory Geriatrics Clinics (Tucker, St. Josephs, and Domiciliary program), Grady's Marcus Stroke and Neuroscience Center, Grady Primary Care, Grady Geriatrics, Assisted Living facilities, Atlanta Adult Day Care facilities, GA Memory Net sites in Augusta, Albany, Macon, and Columbus, Alzheimer's Association early stage program, Atlanta Regional Commission, Northwestern University and Rush University.

In addition to the possible recruitment strategy listed under Stage 1A, another strategy for recruitment will be to review the medical records of **patients seen at the above clinics**. Patient medical records will be reviewed to determine eligibility (a through c of inclusion criteria). Study staff will identify patients deemed eligible, and at the patient's next appointment, the patient's care provider will gain permission for the study staff to explain the study. As stated above, study staff will then obtain verbal consent to administer the UBACC to screen the patient for decision-making capacity. With a patient who has met the UBACC criterion, the recruiter will determine whether the person accompanying the patient is an appropriate surrogate decision-maker using the Surrogate Selection Guide. Written consent will be obtained from each member of the dyad. If the surrogate decision-maker is not present at the time of the visit, study staff will offer consent to the patient and then obtain the name and phone number of the surrogate. Study staff will then call the surrogate within 2 days of the consent visit to assess the surrogate's willingness to participate.

We may also periodically receive lists of eligible patients from providers who have introduced the study to the patient at the time of a visit. In that case, we will follow up by phone with the surrogate and arrange a time to

offer consent to the dyad at the clinic or over the phone. At the time of return clinic visit, study staff will review medical records to determine eligibility (a through c of inclusion criteria, and d of exclusion criteria). If this is not possible due to SARS-COV2, eligibility will be determined using screening methods over the phone. If eligible, study staff will follow the above procedures regarding UBACC screening, confirming the surrogate decision maker, and consenting each member of the dyad.

To recruit participants through Emory's domiciliary program, a study invitation letter signed by the domiciliary program director and PI will be mailed to patients/family caregivers. As done in Stage 1A, this letter will explain briefly about the study and include the research staff contact information and an opt-out postcard. After 2 weeks, a research staff member will review the medical records of domiciliary program patients/families who have not returned the opt-out postcard to screen for eligibility (i.e., dementia diagnosis and MoCA score). If they have met the criteria, the research staff member will call potential patient and/or family caregiver participants to explain the study further and schedule a screening and informed consent meeting at the assisted living facility.

To recruit participants at the assisted living and independent living facilities who are not currently enrolled in the domiciliary program, study staff members may receive recommendations from facility employees. In these cases, study staff will follow the same procedure listed for Emory domiciliary patients (i.e. mailing a letter with an opt-out card and contacting those who do not return the opt out card). We may also receive direct referrals from facility staff who will introduce the study and gain permission from residents and their families to be contacted by a study team member. Study staff members will additionally advertise the study in facility newsletters and/or attend family events at the community to introduce the study to residents and their family members. Study brochures will be made available at these events. Individuals who express interest at these events will be asked to provide contact information. A study staff member will follow up with the interested party and determine eligibility for the study through a screening and informed consent meeting.

To recruit participants from GA Memory Net sites, the Community Services Educator (CSE) at the site will first identify patients who have been diagnosed with dementia and meet the MoCA criterion. When the potentially eligible patient and caregiver make a second visit to the memory assessment center (per GA Memory Net protocol), the CSE will briefly introduce the study to the patient and caregiver (using a script) and ask permission to release their names and contact information (including mailing address) if they are interested in learning more about the study from the research staff. Study brochures will also be made available at the site. Upon the receipt of names and contact information, the research staff will mail a copy of consent form before contacting. A research staff member will call the dyad to explain the study further, determine the remaining eligibility criteria (e.g., UBACC) and proceed informed consent if eligible.

To recruit participants from other recruitment avenues (adult day care programs, Alzheimer's Association early stage program), study staff may send an invitation letter with the program's permission. This invitation letter will follow the same procedures listed for Emory domiciliary patients (i.e. mailing a letter with an opt-out card and contacting those who do not return an opt-out card). Direct referrals may also be received from facility staff members as appropriate. Study staff may additionally coordinate IRB approved study advertisements to be placed in the facility (including newsletters). If appropriate and with permission from the program, study staff will introduce the study at the program's events. Individuals who express interest through these methods will be asked to provide contact information, and study staff members will subsequently follow-up with those individuals. We will also disseminate advertisements through program newsletters (in paper or electronic form).

In the case of Atlanta Regional Commission/AAA), the county case manager, who typically knows the patient's dementia severity and availability of family caregiver, will identify patients/caregivers who are likely to meet the study eligibility criteria. When the case manager is in contact with the caregiver, he/she will briefly introduce the study to the patient and caregiver (using a script) and ask permission to release their names and contact

information (including mailing address) if they are interested in learning more about the study from the research staff. Study brochures will also be made available at the site. Upon the receipt of names and contact information, the research staff will mail a copy of consent form before contacting. A research staff member will call the dyad to explain the study further, determine the remaining eligibility criteria (e.g., UBACC) and proceed informed consent if eligible.

Because adult day care programs and other community organizations are social services, they typically may not keep health records. In the cases where a dementia diagnosis cannot be confirmed from reliable sources, study staff will administer screening questions and a valid questionnaire, "Short Form of the Informant Questionnaire on Cognitive Decline in the Elderly (Short IQCODE)", to the family caregiver to determine whether a patient's cognitive impairment is likely dementia or due to other neurodegenerative condition. The initial screening questions will consist of the following questions:

- Has your loved one been evaluated for memory problems at the doctor's office?
 - If yes, what was the formal diagnosis at that time?
 - Do you have any test results related to the diagnosis?
- Does your loved one take any cognition- enhancing drugs, such as Aricept, Exelon, Reminyl, Namenda, or Provigil?
- Has your loved one had a stroke before this memory problem?

If a caregiver reports their loved one as having dementia based on the screening question and IQCODE (a score 3.3 or higher), study staff will schedule a meeting to determine full eligibility of their loved one and consent.

To recruit participants from Northwestern University and Rush University Alzheimer's Disease Research Center, the co-investigators, [name] at Rush and [name] at Northwestern, will identify patients who are deemed eligible for the study. Their research staff will phone the potential patient participants (and their family caregivers/potential surrogate participants) to introduce the study and gain permission to share contact information with Emory research staff. Upon receiving referrals, Emory research staff will contact these potential participants by phone or email to determine interest and eligibility, explain the study in detail and obtain verbal consent using Verbal Informed Consent/HIPAA authorization format.

For all recruitment sites, the location for consent meeting can be flexible to meet the demands of participants.

